Version 2 (09.01.2012)	
Changes implemented upon recommendation by the independent ethics committee TU Munich:
 
 Section 1.3 & 5.1: 
 The data safety monitoring board will monitor patient safety more thoroughly The first 10 patients will complete the in-patient phase sequentially at a single study centre Section 10.12.2: Corimmun abstains from holding overall right to veto publications and presentations.
Version 3 (22.02.2012)	
Changes implemented upon recommendation by the regulatory authority:
 
 Section synopsis and 5.2.2: 
 Stricter eligibility criterion for enrolment of hypertensive patients implemented and statement on management of hypertension added Stricter eligibility criterion for ECG abnormalities implemented
Version 4 (16.05.2012)	
Changes implemented upon recommendation by the regulatory authority:
 
 Section 6.1.6: An in-line filter must be inserted in the syringe pump infusion line during treatment administration. 
Administrative changes:
 
 Section 6.1.7 and 6.2: Emergency unblinding will be performed using the web-based online randomisation tool. Section 7.2.12: ADP and TRAP concentrations no longer specified due to use of different instruments at individual study sites
Version 5 (26.06.2012)	
 Change of Sponsor from Corimmun GmbH to advanceCOR GmbH
Version 6 (28.09.2012)	
 Section Synopsis, Fehler! Verweisquelle konnte nicht gefunden werden., 7.1, 7.2.12: PFA100 and/or platelet aggregation will be performed at all sites capable of performing the said analysis. Section 5.1: Sequential treatment of the first 10 patients is not restricted to a single study site. Section 5.2.2: Patients who have received tirofiban/Aggrastat are eligible for study participation 8 hours after receiving the said anti-platelet agent
Version 7.1 (15.04.2013)	
Substantial changes:
 
 Section synopsis, Fehler! Verweisquelle konnte nicht gefunden werden., 7.2.6 and Appendix A: Amaurosis fugax assessed as secondary endpoint Section synopsis, 5.2.1 and 6.1.7: 
 European Carotid Surgery Trial (ECST) criteria used for grading of carotid stenosis (instead of North American Symptomatic Carotid Endarterectomy Trial criteria) Patients with Amaurosis fugax (subgroup of TIA) included in study population Flow velocity not assessed as inclusion criterion Section 7.2.10: Troponin may be determined instead of CK 
Non-substantial changes:
 
 Section 1.3: Change of address of DSMB member Section synopsis and 5.1: Wording 'carotid endarterectomy' changed to more general definition of intervention Section synopsis, 5.2.1 and 6.1.7: 
 Wording of exclusion criterion haemorrhagic transformation corrected Section synopsis, 7.1 and 7.2.5: Wound healing complications included in general assessment of adverse events Section 7.2.7: Change of address of TCD core lab Several locations throughout document: 
 thrombocyte function may be analysed by PFA-100 or newer PFA-200 device
Version 7.2 (08.08.2013)	
Non-substantial change:
 
 Section 8.3.1: Update of SAE fax number
Version 7.3 (12.09.2013)	
 Section 8.1 and 8.3.1: SAE, SAR and SUSAR reporting period for PIs set to 24 hours.
Version 7.4 (22.07.2014)	
 Section Synopsis and 5.2.2: Modification of eligibility criteria. Section 1.3: Change of DSMB meeting interval
Version 8 (22.06.2015)	
Change to exploratory study design due to low incidence of MES (i.e. high screening failure rates) upon recommendation by the DSMB (section Synopsis, section 3, 5 and 9 and minor changes for consistency throughout document).

SYNOPSIS

Name of Sponsor:
 
advanceCOR GmbH [name] [name] Germany
	
Coordinating Investigator:
 
PD Dr. med. [name] Department of Neurology TU München [name] [name] Germany


Title of study:
 
Revacept, an inhibitor of platelet adhesion in symptomatic carotid stenosis: A phase II, multicentre, randomised, dose-finding, double-blind and placebo-controlled superiority study with parallel groups.
	

Protocol identification (code or number):
 
Revacept/CS/02
	

OBJECTIVES
 
Efficacy objectives are:
 
 • Assessment of incidence of microembolic signals (MES) by transcranial Doppler (TCD) examination (before and after treatment) • Rate of MES per hour (before and after treatment) • Cerebral lesion analysis by DWI-NMR • Assessment of neurological status (NIH Stroke Scale) • Clinical endpoints will be summarised cumulatively i.e. before treatment, after treatment, at 3 months and at 12 months. The following endpoints will be recorded: 
 ○ Rate of all cause death ○ Rate of stroke-related death ○ Any TIA, amaurosis fugax or stroke including haemorrhagic stroke • Assessment of cardiovascular outcome including myocardial infarction and re-intervention up to 3 and 12 months 	

Safety objectives are to investigate whether Revacept compared to placebo induces adverse and serious adverse events.

Haemostasis will be closely monitored by assessing:

- laboratory parameters indicating thrombocytopenia and bleeding according to the RE-LY study group criteria
- where feasible: in vitro platelet function with collagen, TRAP and ADP-mediated platelet aggregation and in vitro bleeding time by PFA-100 / PFA-200

Pharmacokinetics of Revacept with respect to drug interaction with other antiplatelet drugs will also be assessed by determining plasma concentrations at various time points after administration of study medication for approximately 20 % of patients.

Methodology:

Multicentre, randomised 2:1, double-blind, placebo controlled, parallel groups, analysis. Blinded evaluation of efficacy and safety endpoints.

Treatment Regime:

Patients suffering from symptomatic carotid artery stenosis, transient ischemic attacks (TIAs), amaurosis fugax or stroke receive either Revacept (single dose) plus antiplatelet monotherapy (Aspirin or Clopidogrel) or monotherapy alone.

Patients receive a single dose of trial medication by intravenous infusion for 20 minutes. Patients are followed up one and three days after treatment, at 3 months and by a telephone interview at 12 months.

Treatment Groups:

150 patients currently receiving standard therapy (aspirin p.o. or Clopidogrel) plus one intravenous injection of:

- Placebo (50 patients)
- 40 mg Revacept (50 patients)
- 120 mg Revacept (50 patients)

Indication, diagnosis and main criteria for inclusion and exclusion:

Main inclusion criteria

- Male and female patients aged >18 years

Diagnosis

- Extracranial carotid artery stenosis (diagnosed by vascular duplex ultrasound peak flow or angiography)
 - Lesions with $\geq 50\%$ stenosis according to the European Carotid Surgery Trial (ECST) criteria
- TIA, amaurosis fugax or stroke within the last 30 days

Main exclusion criteria:

Target disease exception

- NIHSS score > 18
- Recent intracerebral haemorrhage by X-ray computed tomography (CT) or nuclear magnetic resonance (NMR)
- Cardiac cause of embolisation (atrial fibrillation or other cardiac source e.g. artificial heart valves)

Medical history and concurrent disease

- History of hypersensitivity, contraindication or serious adverse reaction to inhibitors of platelet aggregation, hypersensitivity to related drugs (cross-allergy) or to any of the excipients in the study drug
- History or evidence of thrombocytopenia ($<30.000/\mu\text{l}$), bleeding diathesis or coagulopathy (pathological international normalised ratio (INR) or activated partial thromboplastin time (aPTT))
- Thrombolysis within the last 48 hours
- Relevant haemorrhagic transformation as determined by CT, NMR or anamnesis
- Oral anticoagulation or dual anti-platelet therapy with aspirin or clopidogrel and other P2Y inhibitors at screening (3 days for dipyridamole extended release; 8 hours for tirofiban/Aggrastat)
- Sustained hypertension (systolic BP >179 mmHg or diastolic BP >109 mmHg)
- History of severe systemic disease such as terminal carcinoma, renal failure (or current creatinine $>200 \mu\text{mol/l}$), cirrhosis, severe dementia, or psychosis
- Current severe liver dysfunction (transaminase level greater than 5-fold over upper normal range limit)
- Active autoimmune disorder such as systemic lupus erythematosus, rheumatoid arthritis, vasculitis or glomerulonephritis
- Known atrial fibrillation or other clinically significant ECG abnormalities (at present)

Trial duration per subject:

Trial duration per subject will be approximately 6 days. Both treatment and control groups are invited for a 3 months follow up visit and a 12 months follow up telephone interview.

Duration of study: The study was initiated in August 2012. The proposed study end is 2017.

Statistical methods:

Since this is an exploratory study, no formal statistical hypothesis testing will be conducted. Descriptive summary of efficacy and safety data will be provided and the data from this study may be combined and analysed with data from future studies.

LIST OF ABBREVIATIONS

ADP	Adenosine Diphosphate		
AE	Adverse event	IEC	Harmonisation Independent Ethics Committee
ANCOVA	Analysis of Covariance	IMP	Investigational Medicinal Product
ANOVA	Analysis of Variance	INR	International normalisation ratio
ASA	Acetyl-Salicylic Acid	ITT	intention-to-treat
aPTT	Activated partial thromboplastin time	LMWH	Low Molecular Weight Heparin
BfArM	Bundesministerium für Arzneimittel und Medizinprodukte	MACE	Major Adverse Cardiac Event
BMBF	Bundesministerium für Bildung und Forschung	MCA	Middle Cerebral Artery
BP	Blood pressure	MES	MicroEmbolic Signals
bpm	beats per minute	MI	Myocardial Infarction
CRF	Case Report Form	MRI	Magnetic Resonance Imaging
CRP	C-reactive protein	MRT	Mean residence time
CT scan	Computerised Tomography scan	MTD	maximum tolerated dose
CV	Curriculum Vitae	NA	Not applicable
D or d	Day	NAV	Not available
DAT	Digital Audio Tape	ND	Not done
DLR	Deutsches Zentrum für Luft- und Raumfahrt	NIHSS	National Institute of Health Stroke Scale
DQF	Data Query Form	OAC	Oral Anti-Coagulant
DSMB	Data Safety Monitoring Board	PP	Per Protocol
DWI	Diffusion-Weighted Imaging	PPP	Platelet Poor Plasma
ECST	European Carotid Surgery Trial	PRP	Platelet Rich Plasma
ECG	Electrocardiogram	PT	Prothrombin time
EDTA	Ethylene diamine tetra- acetate	RBC	Red Blood Cell
ESR	Expedited Safety Report	RRR	Relative Risk Reduction
EU	European Union	SAE	Serious adverse event
FSH	Follicle Stimulating Hormone	SOC	System Organ Class
FWER	Family-wise Error Rate	SUSAR	Suspected Unexpected Serious Adverse Event
GCP	Good Clinical Practice	TAT	Thrombin-Antithrombin III
GI	Gastro-Intestinal	TCD	TransCranial Doppler
GP	General Practitioner	TIA	Transient Ischaemic Attack
Hr or hrs	hour or hours	tmax	Time to Cmax
ICA	Internal Carotid Artery	UFH	UnFractionated Heparin
ICH	International Conference of	WBC	White Blood Cell
		WOCBP	Women of Childbearing Potential

1.3. Data Safety Monitoring Board

The Data Safety Monitoring Board (DSMB) will consist of a statistician together with two independent neurologists who are scientifically well qualified, and who have personal experience of large multicentre studies and data monitoring activities.

Chairman:

[name]. med. [name]
[name]
[name]
[contact]
[contact]

Members:

[name]. [name]
[name]
[name]
[contact]
[contact]

[name]. rer. nat. [name]
[name]
[name]
[contact]
[contact]

The DSMB will hold regular meetings to review data concerning safety, efficacy and study performance. Unblinded data describing clinical endpoints, adverse events and laboratory values are to be compiled for these meetings by d.s.h. statistical services. The DSMB will

inform and advise the sponsor of all findings with regard to safety, efficacy and study performance. Review of data can lead the DSMB to a recommendation to the sponsor to stop the study. Minutes of Committee meetings will be recorded and filed. A special charter for the DSMB evaluation will be available. In accordance to GCP-V §13, SUSARS will be reported to the ethics committee, regulatory authority and the DSMB. If serious adverse events are more common in the experimental arm compared to the control arm the risk/benefit consideration will be reassessed. The Committee will inform the sponsor in writing if the frequency of serious adverse events including deaths exceeds 8 percent in one of the groups, and will advise concerning appropriate actions.

The first safety analysis will be performed by the DSMB once 10 patients have completed visit 5. The first 10 patients will be treated sequentially, e.g. only one patient is randomised at a time. The next patient will be randomised only once the first patient has completed visit 5 and no suspected unexpected serious adverse event has occurred (see also section 5.1). In addition, patient randomisation will be stopped by advanceCOR each time a serious adverse event occurs which is unexpected and possibly related to the study medication (SUSAR, see also section 8.3.2). Patient randomization will be resumed only if recommended by the DSMB. Thereafter, the DSMB will perform safety analysis at least annually.

2. INTRODUCTION AND STUDY RATIONALE

Evidence supporting the idea that microemboli accompany transient ischaemic attacks (TIAs), amaurosis fugax and stroke is rapidly accumulating and it is now generally accepted that such microemboli originate at the site of vascular stenosis (Sitzer et al., 1995, Siebler et al., 1992). These microemboli are made up of platelet aggregates that form by two major mechanisms. Firstly, when atherosclerotic plaques ulcerate and rupture, subendothelial tissues expose factors of high platelet-activating potential. Secondly, platelet adhesion and activation at the site of stenosis is greatly facilitated by increased shear stress resulting from blood flow turbulences in atherosclerotic vasculature (Lassila et al., 1990).

In patients with symptomatic stenoses of the internal carotid artery (ICA), a large number of microemboli enter the cerebral circulation, thereby potentially producing a symptomatic clinical event. They can be detected by Transcranial Doppler (TCD) in the form of characteristic microembolic signals (MES) (Ringelstein et al. 1998). Several studies have demonstrated that the incidence of MES is a potent prognostic factor for prediction of future strokes and TIAs in patients with systematic stenosis, i.e. the risk being 8 to 31 fold higher for MES positive patients than for MES negative patients (Valton et al., 1998, Molloy et al. 1999, Siebler et al., 1995).

Patients suffering a TIA or stroke are at 30-35 % risk of suffering recurrent stroke within the next 5 years and are advised to undergo vascular surgery in order to reduce the risk of future brain infarction (NASCET Collaborators 1991). In addition to surgical carotid endarterectomy (CEA), administration of antiplatelet agents also favours event free survival and reduces MES frequency in patients undergoing carotid endarterectomy (CEA) (Molloy et al., 1998) and in patients with symptomatic carotid stenosis (Goertler et al., 1999).

Although current antiplatelet agents do reduce the risks for recurrent stroke during and after CEA, their use is associated with potentially life-threatening bleeding complications. It is therefore highly desirable to develop novel therapeutic strategies that selectively inhibit thromboembolisation at the site of vascular stenosis whilst not compromising systemic haemostasis.

Such selectivity can be achieved by targeting structures that differ between healthy and atherosclerotic vasculature. Collagen is an important component of the extracellular matrix of arterial walls and thus shielded from the blood stream by the vascular endothelium under normal conditions. Upon vascular injury or atherosclerotic transformation, however, collagen becomes increasingly exposed to the arterial lumen where it triggers platelet aggregation by activating the GPVI receptor on thrombocytes (Nieswandt et al., 2003). By masking collagen exposure to the blood stream at the site of atherosclerotic plaques rather than directly inhibiting thrombocytes, one could prevent local thrombosis without jeopardising systemic platelet functions and coagulation, which is the strategy investigated in this clinical trial. Revacept is a protein that is made up of an Fc (fragment crystallisable) fragment fused to the GPVI receptor (an endogenous platelet collagen receptor). Consequently, Revacept binds to its ligand (collagen) on atherosclerotic plaques preventing circulating thrombocytes from binding to collagen exposed by the injured plaque, most importantly not impairing general thrombocyte activity in animal models (Massberg et al., 2004).

The mode of action of Revacept was studied in animal models in great detail (Massberg et al., 2004, Schönberger et al., 2008, Bültmann et al., 2010). When arterial lesions were induced in mice models of atherosclerosis, Revacept was effective at preventing platelet adhesion and thrombus formation at these sites without affecting bleeding time. Furthermore, bleeding times were not increased when Revacept was combined with

conventional antiplatelet agents such as ASA, clopidogrel and heparin. Furthermore, Revacept is characterised by a promising pharmacovigilance profile with no toxicities or signs of aberrant immune activation detected in preclinical animal studies even after repeated dosing (see Investigator Brochure for more detailed information).

Following these encouraging preclinical studies, safety and tolerability of Revacept was investigated in a first-in-man study (Ungerer et al., 2011). In a phase I clinical trial, 30 male human volunteers received a single intravenous dose of Revacept ranging between 10-160 mg. All investigated doses were well tolerated and no drug-related side effects occurred. Moreover, no anti-Revacept antibodies were produced and favourable pharmacokinetic and pharmacodynamic profiles were observed. In summary, results from both preclinical studies and the phase I clinical trial constitute a solid basis for proceeding to a clinical trial in the target patient population. The study presented here aims to demonstrate both safety and evidence of efficacy of Revacept treatment in patients suffering from symptomatic carotid stenosis.

Dose selection rationale

Detailed background information on preclinical pharmacology, pharmacokinetics, toxicology and on the phase I clinical study of Revacept is provided in the Investigator Brochure. When 10 – 160 mg Revacept were administered during a phase I clinical trial, maximal pharmacodynamic effects were measured *ex vivo*, starting at 40 mg, and no drug-related adverse events occurred. Pharmacokinetic studies demonstrated that the area under the curve and maximum concentration proportionally increased with higher dose levels. Because no maximum tolerated dose (MTD) was defined for the adult population and with data generated during preclinical and phase I studies we propose that maximal therapeutic effect is achieved with low to medium doses of Revacept (40 mg and 120 mg).

Overall risk/benefit assessment

Revacept is a novel therapeutic agent that potently inhibits platelet aggregation at the site of atherosclerotic plaques without compromising systemic coagulation in animal models and healthy volunteers. No toxicities were observed during preclinical studies and no adverse reactions were observed when Revacept was administered to healthy human volunteers. Consequently, safety concerns are limited to adverse reactions specific to the target patient population and rare side effects.

As for all antiplatelet drugs, it cannot be entirely excluded at this stage of development that Revacept could potentially increase bleeding propensity. Especially the likelihood of bleeding problems might occur in combination with multiple anti-thrombotic or antiplatelet drugs. In order to keep this risk low, concomitant oral anticoagulation and antiplatelet drugs other than anti-thrombotic monotherapy with Aspirin or Clopidogrel are prohibited in this study.

The immunogenicity of Revacept is judged to be considerably low, as its components are naturally occurring in the human body and should hence be recognised as 'self'. As for all therapeutic proteins, there is residual risk for Revacept triggering an aberrant immune reaction. Potential allergic responses may produce mild symptoms such as skin rashes and flue-like symptoms but also severe and potentially life-threatening reactions such as anaphylactic shocks. In order to minimise the risk of acute allergic reactions, patients with a history of allergic responses to intravenously administered drugs will be excluded from study participation. Furthermore, all patients will remain under medical supervision for 24 hours after receiving study medication.

Although the risk for production of anti-drug antibodies is low for single dose application, anti-Revacept autoantibodies could potentially cross-react with circulating platelets. For minimisation of this risk, patients with a known history of thrombocytopenia will not be

allowed to participate in this study. Furthermore, platelet counts and bleeding time will be closely monitored throughout the trial and blood samples for determination of anti-drug antibodies will be collected before and 3 months after exposure to study treatment.

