5.2.2. Exclusion Criteria

Subjects must not be included for any of the following reasons:

1) Sex and reproductive Status:

- WOCBP who are unwilling or unable to use an acceptable method to avoid pregnancy for up to 4 weeks after receiving investigational product.
- Women who are pregnant or breastfeeding
- Women with a positive pregnancy test on enrolment or prior to investigational product administration.

2) Target disease exceptions

- NIHSS score > 18
- Recent intracerebral haemorrhage by X-ray computed tomography (CT) or nuclear magnetic resonance (NMR)
- Cardiac cause of embolisation (atrial fibrillation or other cardiac source e.g. artificial

heart valves)

3) Medical history and concurrent disease

- History of hypersensitivity, contraindication or serious adverse reaction to inhibitors of platelet aggregation, hypersensitivity to related drugs (cross-allergy) or to any of the excipients in the study drug
- History or evidence of thrombocytopenia ($<30.000/\mu\text{l}$), bleeding diathesis or coagulopathy (pathological international normalised ratio (INR) or activated partial thromboplastin time (aPTT))
- Thrombolysis within the last 48 hours
- Relevant haemorrhagic transformation as determined by CT, NMR or anamnesis
- Oral anticoagulation or dual anti-platelet therapy with aspirin or clopidogrel and other P2Y inhibitors at screening (3 days for dipyridamole extended release; 8 hours for tirofiban/Aggrastat)
- Sustained hypertension (systolic BP >179 mmHg or diastolic BP >109 mmHg), hypertensive patients shall be treated in accordance with current guidelines for the management of arterial hypertension
- History of severe systemic disease such as terminal carcinoma, renal failure (or current creatinine >200 $\mu\text{mol/l}$), cirrhosis, severe dementia, or psychosis
- Current severe liver dysfunction (transaminase level greater than 5-fold over upper normal range limit)
- Active autoimmune disorder such as systemic lupus erythematosus, rheumatoid arthritis, vasculitis or glomerulonephritis
- Known atrial fibrillation or other clinically significant ECG abnormalities (at present)

4) Other Exclusion criteria

- Inability to provide informed consent (except for patient's legally responsible representative)
- Acoustic window that does not allow for TCD recording
- Participation in any other interventional study within less than 30 days prior to screening
- Suspected poor capability to follow instructions and cooperate

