6.1.7. Randomisation

Patients will be assigned to a treatment group by web-based online randomisation. Each patient will be allocated to one of the three treatment arms using a minimised randomisation method in order to balance potential prognostic factors between individual treatment arms. The following stratification factors will impact on treatment allocation:

- (1) Patient has received anti-platelet therapy with aspirin or clopidogrel prior to screening
 - No
 - Yes
- (2) Patient has received statin therapy prior to screening
 - No
 - Yes
- (3) Degree of carotid stenosis (ECST criteria)
 - 50-70%
 - > 70%

Once a patient is found to fulfil all eligibility criteria of the study the patient's identification number and details on concomitant medication are submitted to a web-based online randomisation program accessible at:

<https://www.randomizer.at/random/web/login.php>

All trial staff involved in patient randomisation will receive their log in data for the program after a short introduction to the system. In order to randomise a new patient, select "randomise" in the control panel on the left, enter the patient number (numeric format, including centre specific prefix, e.g. 01-005), select the applicable stratification

factors and click "randomise".

In case a reduced set of medication kit boxes is available at the study centre (e.g. due to damage or expiry of trial medication), you may tick option "reduced set of treatments", select "next", highlight all **unavailable** kit box numbers and then click on "randomise".

After successful randomisation of a patient, the web-based online system will send a confirmation email to the person who randomised the patient which contains the patient-specific random kit box number. This confirmation is to be printed, dated, signed and filed in the Investigator Site file.

Please check the number of remaining IMP kit boxes after each patient enrolment and make sure to request additional supplies as soon as less than 10 kit boxes remain, or earlier, in case of high recruitment rates.

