7.2.7. Transcranial Doppler

Central Analysis & Test Run

Each study centre shall send a test dataset to the central core laboratory prior to starting patient recruitment. The core lab will notify the study centre and sponsor of successful completion of a test run. TCD recordings are to be sent to the following core lab for central analysis:

PD Dr. med. [name]
Facharzt für Neurologie
[name]
[name]
[contact]
[contact]

Central analysis will be performed for both TCD datasets recorded for each patient enrolled (i.e. visit 1 and 3).

There is no need for local analysis of TCD recordings. Both TCD recordings are analysed centrally only.

MES detection by TCD

TCD recordings will be made from the middle cerebral artery (MCA), via the trans-temporal route. Each TCD assessment is recorded for one hour as specified below.

All TCD recordings must be performed under similar conditions, i.e.:

- Same apparatus
- Same position of patient
- System settings

All recordings shall be performed with a DWL TCD machine with single-depth 2-MHz transducers. Standard settings should be used. Machine settings shall be adapted to harmonised consensus guidelines (Ringelstein et al., 1998) and agreed upon by all study centers. For TCD recording, patients are to be placed in a sitting or supine position. The MCS will be identified via transtemporal window and a transducer will be attached using a

standard headset. TCD signals are recorded for one hour. The total number of MES per hour will be analysed.

Spectral display and audio signals will be monitored acoustically and visually online by an experienced observer during all recordings. Audio and visual signals will be recorded onto suitable storage media for central analysis.

MES will be identified visually as predominantly unidirectional short-duration intensity increase accompanied by characteristic acoustic clicking, chirping or moaning sounds. A previously agreed threshold will be set at all participating study centres following validation by analysis of standard reference tapes. MES intensity will be measured in dB and be calculated as the ratio of peak intensity of MES divided by the intensity of the background signal. The same algorithm will be used throughout the study. Central offline analysis of all recordings will be performed using the same machine and same algorithm.

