### **8.2.8 TCD**

The result of the TCD central assessment ([name], Münster) is a key element for the efficacy analysis of the study, see 8.4

The technical possibility to perform TCD (sufficient bone window) determines whether a patient is eligible for the study.

- TCD assessment was successful

Due to high rate of no microembolic signals we abandoned the criterion that if no microembolic signal was detected during the recording period then the patient was rated not eligible during the course of the study. In the further course of the study patients were included irrespective whether they present with microemboli or not.

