#### **8.4.5 Clinical endpoints summarised cumulatively i.e. before treatment, before CEA, 1 day after CEA, at 3 months and at 12 months.**

For the following endpoints

- Rate of all cause death
- Rate of stroke-related death
- Any TIA or stroke including haemorrhagic stroke
- Rate of Myocardial infarctions and coronary re-intervention

the number of patients will be summarized by means of frequency tables. Groups will be compared using Fisher's exact test.

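### Stroke/TIA comparisons ignore baseline MES status, which came to vary once MES-negative patients were admitted: a modest loss of precision that a prespecified stratified sensitivity analysis would recover

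*Protocol*

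**What the plan says.** - **Prognosis.** Protocol section 2 states that "the incidence of MES is a potent prognostic factor for prediction of future strokes and TIAs" in its disease setting, "the risk being 8 to 31 fold higher for MES positive patients than for MES negative patients". It gives no prognostic ratio for any other baseline factor.
- **Entry.** SAP 8.2.8 explains that patients without MES were at first ineligible and that this rule was dropped: "In the further course of the study patients were included irrespective whether they present with microemboli or not". The current exclusion list in protocol 5.2.2 keeps only a technical TCD requirement ("Acoustic window that does not allow for TCD recording").
- **Allocation.** Protocol 6.1.7 describes minimisation "in order to balance potential prognostic factors between individual treatment arms". The factors, repeated in SAP 3.1, are prior antiplatelet therapy, prior statin therapy and degree of stenosis.
- **Clinical endpoints.** For deaths, TIA or stroke, and MI or coronary re-intervention, SAP 8.4.5 says: "Groups will be compared using Fisher's exact test". SAP 8.4.6 analyses the combined ischaemic endpoint by Cochran-Mantel-Haenszel, with rescue medication (yes/no) as the only stratum.
- **Other adjustment.** The conditional stratified analyses in SAP 8.4.1 cover the first (MES) endpoint only. Their list of baseline parameters (demographics, medical history, blood pressure, physical examination) omits MES.
- **Baseline description.** SAP 8.2.8 plans no between-arm comparison of Visit 1 MES, whereas SAP 8.2.9 plans one for DWI lesions. SAP 8.4.2 does summarise the MES rate at Visit 1.

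**The concern.** While every patient had to be MES positive, MES status could not differ between arms. Once the rule was dropped, the trial became a mixture of two groups whose stroke/TIA risk, on the protocol's account, differs severalfold. The analysis of the clinical endpoints was not updated to match. An arm that happens to receive more MES-positive patients will tend to show more events whatever the drug does, and with few events a crude table cannot separate the two. The covariate that would do so is recorded before treatment and read centrally. The estimates also have a life beyond this trial, because the synopsis says the data may be combined with those of future studies.

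**Working it through.** **The plan's own figure.** The documents give no alpha, power, event rate or effect size behind 50 per arm, so only the totals can be checked: 3 × 50 = 150, and 100:50 = 2:1. Both agree.

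**Inputs from the documents.** 50 per arm (SAP 3.3). Risk ratio R = 8, the lower end of the protocol's range.

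**Assumptions.** MES-positive share f = 10-40%; overall stroke/TIA rate p = 6-10%; allocation independent of MES status.

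**Formulas** for two arms of 50:
- SD of the difference in MES-positive share = √[2f(1−f)/50]
- Risk in MES-negative patients r0 = p/(1−f+fR); in MES-positive patients r1 = R·r0
- Shift in crude risk difference at a 1.96-SD imbalance = 1.96 × SD × (r1−r0)
- Share of outcome variance explained = f(1−f)(r1−r0)²/[p(1−p)]
- Reduction in standard error = 1 − √(1 − share explained)

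**Example**, f = 10%, p = 10%: SD = √(2 × 0.1 × 0.9/50) = 0.060. r0 = 0.10/(0.9+0.8) = 0.0588 and r1 = 0.4706. Shift = 1.96 × 0.060 × 0.4118 = 4.8 points. Share explained = 0.09 × 0.4118²/0.09 = 17.0%. Reduction = 1 − √0.830 = 8.9%.

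| f | SD (points) | p | r0 / r1 (%) | Shift (points) | Variance explained | SE reduction |
|---|---|---|---|---|---|---|
| 10% | 6.0 | 6% | 3.5 / 28.2 | 2.9 | 9.7% | 5.0% |
| 10% | 6.0 | 10% | 5.9 / 47.1 | 4.8 | 17.0% | 8.9% |
| 20% | 8.0 | 6% | 2.5 / 20.0 | 2.7 | 8.7% | 4.4% |
| 20% | 8.0 | 10% | 4.2 / 33.3 | 4.6 | 15.1% | 7.9% |
| 30% | 9.2 | 6% | 1.9 / 15.5 | 2.4 | 6.8% | 3.5% |
| 30% | 9.2 | 10% | 3.2 / 25.8 | 4.1 | 11.9% | 6.1% |
| 40% | 9.8 | 6% | 1.6 / 12.6 | 2.1 | 5.2% | 2.6% |
| 40% | 9.8 | 10% | 2.6 / 21.1 | 3.5 | 9.0% | 4.6% |

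**Scale.** The standard error of the crude risk difference is √[2p(1−p)/50] = 4.7 points (p = 6%) to 6.0 points (p = 10%), a 95% half-width of 9.3 to 11.8. The shift is a part of that error and is not added to it.

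**How often.** By exact binomial calculation, two arms of 50 differ by at least 10 points in MES-positive share in 13%, 26%, 33% and 36% of allocations at f = 10, 20, 30 and 40%.

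**Test behaviour.** Simulation of 100 active v 50 placebo, 8 fold, f = 20-30%, 20,000 runs per scenario, two-sided 5% level:
- No drug effect: unstratified Fisher rejects in 3-4%; the MES-stratified Mantel-Haenszel test in 4.7-4.9%.
- No drug effect, MES-positive share fixed at 22% v 32%: Fisher 5-6%, unstratified Mantel-Haenszel 7-8%, stratified about 5%.
- Assumed true risk ratio 0.4, 10% overall risk: power is about 27% (Fisher), 31% (unstratified Mantel-Haenszel) and 33-34% (stratified). At 20% overall risk it is 49%, 57% and 63-65%. Part of the gain over Fisher is therefore Fisher's own conservatism.

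**The case against.** Most of the case against bears on the weight of the point.

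- **No bias.** Randomisation keeps the crude comparison valid on average, and the simulation shows no inflation. A reader might infer that omitting MES biases the stroke/TIA result. The documents do not support that.
- **Transfer of the ratio.** The protocol quotes 8 to 31 fold for prediction of future events. One of its three sources is, by title, a study of asymptomatic high-grade stenosis, while this trial enrols symptomatic patients, schedules CEA or another intervention about three days after treatment where applicable, and counts events to 12 months. Nothing says the ratio persists once the stenosis is treated. This stands, and is why the sizes here use 8 fold and may still be too large.
- **The upper end.** At 31 fold the same formulas reach an 8.8-point shift and 56% of variance, but only at f = 10% and p = 10%, which implies a 77.5% event rate in MES-positive patients. Those figures should not be used.
- **Minimisation.** A reader might conclude that MES should become a fourth factor. The SAP, dated 10.06.2019, describes randomisation in the past tense. Protocol 7.2.7 has an observer at each recording ("Spectral display and audio signals will be monitored acoustically and visually online by an experienced observer during all recordings") but says the recordings are analysed centrally only, so a bedside call would be a new local reading. This is not pursued.
- **Baseline display.** SAP 8.4.2 already summarises Visit 1 MES, and SAP 8.2 promises all important screening characteristics. Only an explicit 0 v >0 table by arm is missing.
- **DWI lesions.** Extending the stratification to new lesions has no support in a ratio stated for stroke and TIA.
- **Exploratory study, few events.** At 6-10% there are 3-5 events per arm of 50, so strata will be sparse. That argues for a sensitivity analysis beside the crude result, not a replacement for it.

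**Conclusion.** The gap is real and modest. The plan treats MES as strongly prognostic and admits patients with and without them, but uses MES status neither in allocation nor in comparing stroke/TIA. The one stratum it does use, rescue medication, is itself post-randomisation. At 8 fold, a large chance imbalance (1.96 SD) moves the crude risk difference by 2.1-4.8 points, and adjustment narrows its standard error by about 3-9%. These sizes rest on an assumed MES-positive share of 10-40%, an assumed event rate of 6-10%, and the protocol's lower ratio holding through follow-up. The documents do not say when the entry rule was dropped or how many MES-negative patients followed. The crude analyses are valid and should stay. The case for adding an adjusted estimate is that it costs almost nothing, and that a stratum named before unblinding is more credible than one chosen afterwards.

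**What to change.** Before the blind is broken, add to SAP 8.4.5 (stroke/TIA) and 8.4.6 (combined ischaemic endpoint) a sensitivity analysis reported beside the planned result: the Mantel-Haenszel risk difference with 95% CI and an exact stratified test, both stratified by centrally read Visit 1 MES (0 v >0). Show the number and percentage of patients with Visit 1 MES 0 and >0 by arm in the same table.

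The cost is a few sentences of SAP text and one table, with no new data, since Visit 1 TCD is recorded before treatment and read centrally in every enrolled patient. The downside is sparse strata. The exact test stays valid there, but with so few events the gain in precision may be small.
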